After smoking their preferred/usual brand in their home environment for 7-days (baseline period) and then in the laboratory ad libitum, participants will undergo two experimental conditions of smoking SPECTRUM menthol and non-menthol very low nicotine cigarettes (VLNCs) (order of administration counterbalanced) in their home environment for 7 days and then in the lab ad libitum. The experimental phases of smoking research VLNCs will be separated by a 7-day wash-out period, where participants will be asked to resume the same amount of smoking as the baseline period. On the last day of each experimental condition, 12-hour abstinent participants will smoke the assigned research cigarette in the laboratory, where data on toxicant exposure (i.e., boost in exhaled carbon monoxide) and smoking topography measures will be collected. Participants will also complete questionnaires about smoking urges, withdrawal, mood, and subjective effects of smoking (satisfaction, psychological reward, sensory effects) immediately before and after smoking a cigarette at each visit. Participants will be compensated \$35 for the baseline session or \$25 if they are deemed ineligible. Participants will be compensated \$45 for laboratory smoking sessions 2-4 if they are eligible and \$50 for session 5. Participants can receive a \$20 bonus incentive if they schedule and attend the first study session with 5 business days of completing the phone screener.

During each 7-day take-home period of smoking SPECTRUM cigarettes, participants will be instructed to switch their usual brand cigarette for the assigned research cigarette and will provide daily data on cigarette use, withdrawal, smoking urge, other tobacco use, and subjective response to smoking via twice daily EMA, as well as other factors related to tobacco use.

Protocol Modifications in Response to COVID-19

To prioritize the participants' and the study team's health, the sequence of study requirements may vary due to COVID-19, rules and guidelines set by authorities at the National, Local, or University level. This may mean that the in-person study visits may become virtual (e.g. online video calls) visits. Per our other IRB approved protocols (10581, 10974), the consent and baseline survey will be collected electronically if a participant chooses virtual sessions. Age will be verified before participants engage in their first smoking session if they complete the study remotely/virtually.

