COVID-19 accommodations for measuring smoking behavior and expired carbon monoxide: Remote topography will be used to allow ambulatory smoking behavior to be recorded remotely from the participant's, if a session is completed remotely/virtually due to COVID-19. The unit will record time, puff duration, volume of smoke inhaled and pressure drops and calculate averages and standard deviations. By using this device, the study will be able to collect smoking topography remotely. Additionally, pregnancy tests will be sent to female participants for exclusion confirmation prior to virtual smoking sessions.

Participants will also be provided a smartphone compatible portable carbon monoxide (CO) monitor (iCO Smokerlyzer) and asked to complete iCOs reading of expired CO to verify smoking status at the beginning of each virtual smoking session ($\leq 6\text{ppm}$ or $>50\%$ reduction in CO from baseline) and exhaled CO (exposure) following smoking. Participants will be prompted to connect the iCO device to the study smartphone at the beginning of each study session. They will follow step-by-step instructions to complete the iCO test provided on the smartphone app, and can be assisted by the study staff member during the video call to ensure the device is used correctly. Results of these tests will be date and time stamped. Each participant will be provided their own iCO Smokerlyzer free of charge. This iCO procedure has been approved for use in several other OUHSC IRB-approved studies.

Research Cigarettes. We will use combustible SPECTRUM research cigarettes available through the NIDA Drug Supply Program. The VLNC non-menthol and menthol cigarettes will both be 0.4 mg nicotine/g tobacco. These nicotine levels were chosen because prior studies have shown that there is a significant reduction in cigarettes smoked per day and biomarkers of nicotine exposure compared to normal nicotine content cigarettes at this level. Further, it has been proposed that the maximum allowable nicotine content of cigarettes by FDA will be roughly equivalent to this level.² The application to obtain research cigarettes from NIDA will be initiated once the OUHSC IRB has approved the study protocol, as a copy of the Institutional Review Board letter is required as part of this application process.

Pre-Screening/Baseline Session (V1):

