Smoking Session 1 (V2): Usual Brand Smoking. At the end of the 7-day baseline period of usual brand smoking, > 12-hour abstinent smokers (expired CO \leq 6ppm) or >50% reduction in CO from baseline, per Co-I [name] research²⁴ will return to the laboratory to assess absolute reinforcing value (ARV) of their usual brand cigarette by having participants smoke one of their usual brand cigarettes (ad libitum) through a transducer-based smoking topography data collection device. The instrument records puff volume, duration and velocity and inter-puff interval for each puff and their aggregate averages. These puff topography measures are useful indices of smoke exposure and are sensitive to differences in smoking behavior that may occur between different cigarette flavoring types.^{59,61,124} Puff topography measures will be used to examine whether increased puff volume, duration, and lower inter-puff interval differ across cigarettes as a measure of compensation. Prior to smoking participants will be asked when they smoked their last cigarette. Immediately before and after smoking the following measurements will be taken: heart rate and blood pressure will be assessed (heart rate, but not blood pressure, will be collected for remote sessions), and exhaled carbon monoxide (CO boost).

Subjective response to smoking (craving reduction, psychological reward, satisfaction, sensory effects) using the **Modified Cigarette Evaluation Questionnaire (mCEQ)**¹³⁸⁻¹⁴⁰ in addition to the **Nicotine Drug Effects Questionnaire (N-DEQ)**, the **Duke Sensory Questionnaire (DSQ)**, and the **Minnesota Nicotine Withdrawal Scale (MNWS)** will be measured immediately after smoking. Exhaled CO will be collected via a Smokerlyzer CO detector (Bedfont Scientific LTD), and measured in ppm immediately before and 10 minutes after smoking. CO boost has been used in previous studies^{141,142,143} to index smoke exposure, and will be calculated as the difference between pre- and post-smoking levels.

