Primary Outcomes: (a) The relative reinforcing value (RRV) of usual brand cigarettes vs menthol VLNCs; (b) RRV of non-menthol VLNCs vs menthol VLNCs. RRV will be operationalized as within-subject differences in subjective ratings of cigarette appeal/reinforcement (satisfaction, reward, craving reduction, physical sensations) during each ad libitum smoking session. Secondary Outcomes: (a) CO boost; and (b) puff topography (number of menthol versus non-menthol cigarette puffs consumed, number of minutes smoked, interval between puffs).

Analysis of covariance will be conducted to examine effects of cigarette type (usual brand, menthol VLNC, non-menthol VLNC) on the outcomes of interest, controlling for cigarettes per day (CPD), nicotine dependence, race/ethnicity, gender, and age of smoking onset as potential covariates. Factors related to study drop-out and differences in cigarette compliance will also be examined as potential covariates. Exploratory analyses will examine differential reactions to usual brand and each research cigarette by race/ethnicity (White, Black, Hispanic, Other) and by gender. Significant interactions will be followed up with individual contrasts of cell means using Fisher's Least Significant Difference tests. We will examine whether topography differs as a function of in-person versus remote session.

3. EMA Analyses (Aim 2)

Primary Outcomes: (a) within-day subjective response (craving reduction, satisfaction, psychological reward, physical sensations like throat grab) to the most recent cigarette smoked; (b) within-day number of research cigarettes smoked per day; (c) within-day number of non-research cigarettes smoked; and (d) within-day withdrawal intensity. Secondary Outcomes: (a) within-day use of alternative tobacco products; (b) changes over the course of days (creating an average change score for each person) for each outcome; (c) number of days abstinent from tobacco use.

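### Session mode (in person or remote) is examined only for topography, so the primary ratings and CO boost may carry a mode effect when mode changes between visits, chiefly in usual brand versus VLNC

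*Combined protocol and SAP*

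**What the plan says.** **Mode can vary by session.** The section on protocol modifications for COVID-19 says of changing rules and guidelines: "This may mean that the in-person study visits may become virtual (e.g. online video calls) visits". The same section provides for a different topography unit session by session: "Remote topography will be used to allow ambulatory smoking behavior to be recorded remotely from the participant's, if a session is completed remotely/virtually due to" [the pandemic].

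**Measurement differs by mode.** Under Smoking Session 1 (V2), laboratory smoking is recorded "through a transducer-based smoking topography data collection device". CO is specified there as follows: "Exhaled CO will be collected via a Smokerlyzer CO detector (Bedfont Scientific LTD), and measured in ppm immediately before and 10 minutes after smoking". For remote sessions the COVID-19 section supplies "a smartphone compatible portable carbon monoxide (CO) monitor (iCO Smokerlyzer"), with a reading after smoking and no interval given.

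**Order.** Usual brand is always smoked at Visit 2. Only the two VLNC flavours, at Visits 3 and 4, are counterbalanced.

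**Analysis.** Section J.2 defines the primary Aim 1 outcome as within-subject differences in ratings, for usual brand versus menthol VLNC and for non-menthol versus menthol VLNC. CO boost and topography are secondary. The potential covariates are cigarettes per day, dependence, race/ethnicity, gender, age of onset, factors related to drop-out, and cigarette compliance. Session mode appears only in the closing sentence: "We will examine whether topography differs as a function of in-person versus remote session".

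**The concern.** The plan accepts that the setting and equipment of a session could influence what is measured, but looks for that influence in one secondary outcome family only. It also plans a comparison of modes there, not an adjustment. The primary ratings get neither, although smoking alone on a video call and smoking in a laboratory room are different settings. CO boost gets neither, although the meter changes.

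Every Aim 1 outcome compares sessions within a person, so a change of mode between two sessions enters the difference directly. Counterbalancing spreads such changes evenly over the two VLNC flavours. It does nothing for usual brand, which is fixed at Visit 2. If sessions drift from remote to in person, or the reverse, as participants move through the schedule, that drift is confounded with usual brand versus VLNC, which is primary outcome (a) of Aim 1.

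**Working it through.** The plan states no figure for the size of this problem, so there is none to reproduce.

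**Inputs from the documents**
- Analysed sample n = 100 (J.1).
- Usual brand at Visit 2, VLNC flavours counterbalanced over Visits 3 and 4 (V2 section).
- CO boost is post-smoking minus pre-smoking within a session (V2 section).

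**Assumptions (not in the documents)**
- Ratings scaled to SD 1 per session, correlation r = 0.5 between two sessions of one person.
- Additive mode effect m = 0.2 to 0.5 SD.
- Net shift in remote share between Visit 2 and Visits 3-4: d = 10 to 20 points.
- Share switching between Visits 3 and 4: s = 20%.

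**1. Mode constant within a person.** The effect m is in both sessions: (a + m) − (b + m) = a − b. The bias is 0 in both primary contrasts, provided the same people contribute both sessions.

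**2. Usual brand versus VLNC when the remote share shifts.** Bias = d × m. The standard error of a mean paired difference is √(2(1 − r)/n) = √(2 × 0.5/100) = 0.10.

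| Shift d | m = 0.2 | m = 0.5 |
|---|---|---|
| 10 points | 0.02 SD (0.2 SE) | 0.05 SD (0.5 SE) |
| 20 points | 0.04 SD (0.4 SE) | 0.10 SD (1.0 SE) |

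A bias of 1 SE would make a nominal two-sided 5% test reject a true null about 17% of the time: P(Z > 0.96) + P(Z < −2.96) = 0.169 + 0.002. At 0.2 SE the figure is about 5.5%: P(Z > 1.76) + P(Z < −2.16) = 0.039 + 0.015.

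**3. Menthol versus non-menthol when 20% switch between Visits 3 and 4.** Half the switchers have each order, so the expected bias is 0. The variance of the difference is 2(1 − 0.5) = 1.0, and switching adds s × m²: 0.2 × 0.04 = 0.008 to 0.2 × 0.25 = 0.05. That is about 1 to 5% more variance. At the top, the standard error rises by √1.05 − 1, about 2.5%.

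**4. Where that protection fails.**
- Flavour-related switching: if 20% go remote for one flavour only, the bias is 0.2 × m = 0.04 to 0.10 SD.
- Mode-by-cigarette interaction: with 40% remote throughout and an interaction of 0.2 SD for menthol VLNC, each contrast involving menthol VLNC shifts by 0.4 × 0.2 = 0.08 SD even though nobody switches.

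**5. CO boost.** Take illustrative readings of 5 ppm before and 11 ppm after, a boost of 6.0. A constant meter offset of 2 ppm gives 13 − 7 = 6.0, unchanged. A proportional difference does not cancel: 1.10 × 6.0 = 6.6 and 1.25 × 6.0 = 7.5.

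**Simulation check** (n = 100, 4,000 runs, SD of the difference about 1; results for m = 0.2 and 0.5):
- Constant mode: 0.00 in both contrasts.
- Remote share falling from 60% at Visit 2 to 40% at Visits 3-4: 0.04 and 0.10 in usual brand versus menthol VLNC.
- The same fall at Visit 4 only, an average shift of 10 points: 0.02 and 0.05.
- In both shifting cases the flavour contrast stayed at 0.00.
- Flavour-related switching gave 0.04 and 0.10 in the flavour contrast, in absolute value.

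**The case against.** The strongest reply is that within-subject differencing already does the work. It does so for participants who keep one mode, for the flavour contrast under counterbalancing, and for a constant CO meter offset. A reader might infer from J.2 that the primary ratings and CO boost do carry an unadjusted mode effect, or that the menthol contrast is biased. The documents support neither. The first needs mode to change between visits, an interaction, or a proportional or timing difference in CO. The second needs flavour-related switching or an interaction.

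A second reply is that parts of the protocol treat mode as a choice made once by the participant: the COVID-19 section and Measures Descriptions both speak of doing the study remotely. That weakens the case for mixing but does not exclude it. Other wording in the COVID-19 section and the V2 section is session by session, and no rule fixes mode within a participant. Bias also needs a net shift in one direction.

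Third, the device change bears most directly on topography, where the plan does look. The ratings are questionnaires with no stated remote form, so only setting could move them. That is fair, and it argues for the lower end of the assumed range.

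Finally, a reader might see a contradiction in CO timing, because the remote paragraph omits the interval "measured in ppm immediately before and 10 minutes after smoking". That goes too far. The V2 section itself names an exception for remote sessions (heart rate without blood pressure) and none for CO timing, so the natural reading is that 10 minutes applies throughout.

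**Conclusion.** The gap is real and minor. Mode is examined for one secondary outcome family and left out of the models for the primary ratings and CO boost. These may carry a mode effect when mode changes between visits. The comparison at risk is usual brand versus VLNC, with a bias of 0.02 to 0.10 SD (0.2 to 1.0 SE at n = 100, r = 0.5). This rests on an assumed mode effect of 0.2 to 0.5 SD and an assumed net shift of 10 to 20 points in remote share. None of these inputs is in the documents, and the sign is unknown. For scale, 100 pairs detect about (1.96 + 0.84)/√100 = 0.28 SD with 80% power at an assumed two-sided 5% level, so the bias would distort a small difference more than a large one. Menthol versus non-menthol is essentially safe, apart from the two exceptions in step 4. The change is worth making because it is cheap, not because a distortion has been shown.

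**What to change.** Replace the closing mode sentence of J.2 with:

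> Session mode (in person/remote) will be recorded at each visit and included as a session-level term in the Aim 1 models for subjective ratings, CO boost and topography, with a mode-by-cigarette-type check. As a sensitivity analysis, contrasts will be repeated in participants whose compared sessions share one mode.

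The protocol should also state whether mode is meant to be fixed within a participant, and say as a clarification that the 10-minute post-smoking CO reading applies to remote sessions too. No participant need be moved from one mode to the other.

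**Cost.** Wording, one parameter for the mode term and two more for the interaction (three cigarette types by two modes). Mode must already be known for the planned topography comparison, although no section says that it is recorded per visit. Precision can suffer. If 20 of 100 participants switch the same way between Visit 2 and the VLNC session, a mode-adjusted paired contrast rests essentially on the other 80, and its standard error rises from 0.10 to 1/√80 = 0.112. The same-mode subset selects on something settled after the cigarette order was assigned, possibly in response to the cigarette, so it should stay a sensitivity analysis and not replace the main one.

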Aim 1: Determine the influence of menthol flavoring on smoking reinforcement in the context of a reduced nicotine standard in the laboratory. Abstinent smokers (> 12 hours) will attend four laboratory visits. Following a 7-day baseline period of usual brand smoking at home, smoking session 1 will measure reinforcement of one's usual brand cigarette via ad-libitum smoking, where subjective response (satisfaction, craving reduction, psychological reward, sensory effects like throat hit), smoking exposure (CO boost), and behavior (number of puffs, puff volume) will be measured. Following smoking session 1, participants will then undergo two experimental conditions (counterbalanced) in their home environment and the lab for 7 days each: (1) 7 days smoking menthol VLNCs; (2) 7 days smoking non-menthol VLNCs. Participants will be instructed to switch their usual cigarette for the assigned cigarette for each 7-day period (allowing for other product use during that time without specific instruction to model real world behavior). Each condition will be separated by a 7-day wash-out period. On the last day of each condition (smoking Visits 2 and 3), participants will smoke the assigned research cigarette in the laboratory, and data on subjective response, smoking exposure, and behavior will be measured. Hypothesis: Craving reduction and positive subjective response will be greater for menthol VLNCs compared to non-menthol VLNCs, but lower compared to usual brand.

Aim 2: Determine the influence of menthol flavoring on smoking reinforcement in the context of a reduced nicotine standard in the natural environment. During each 7-day period of exposure, participants will complete assessments of cigarette and other tobacco use, withdrawal, and subjective response (satisfaction, craving reduction, reward, sensory effects) via twice-daily EMA. Hypothesis: Cigarettes per day, craving reduction, and positive subjective response will be greater for menthol versus non-menthol VLNCs, but lower compared to usual brand. Per previous work, ATP use will be greater in both VLNC conditions compared to usual brand. Effects of menthol vs non-menthol VLNCs on withdrawal, mood, cigarette compliance, and ATP will be compared.

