This proposal will answer important policy relevant questions about the ways in which menthol smokers could be influenced by FDAs regulatory actions to bring VLNCs to the market AND ban menthol in combustible cigarettes. If smoking menthol VLNCs translates into greater appeal and cigarette consumption relative to smoking non-menthol VLNCs in YAs and adults aged 26-34 who are new to smoking, this provides further evidence that menthol in cigarettes, even with low levels of nicotine, could be a public health hazard. This would support FDA’s authority to take additional regulatory actions toward the distribution, manufacture, or marketing of menthol to improve public health. These actions

could include extending the flavored cigarette ban to cigarettes (distribution), restricting menthol cigarette sales to adult-only venues (distribution), limiting the amount of menthol allowed in cigarettes (manufacture), and reducing menthol appeal through public health campaigns or warnings (marketing).

Conceptual Framework and Scientific Premise.

The scientific premise for this study relies on Dual-Reinforcement Model of Smoking.³⁴ According to this model, nicotine has two key effects on reinforced behavior: (1) nicotine acts as a primary (unconditioned reinforcer) that can support the establishment of associated stimuli as conditioned reinforcers, and (2) nicotine enhances the effectiveness and reward value of non-nicotine reinforcers directly, through non-associative mechanisms. The latter is exemplified by studies in which nicotine, administered in a manner unrelated to any cues or behavior, increases operant responding for both unconditioned and conditioned reinforcers.³⁵⁻³⁸ As applied to the current study, this model proposes that menthol smoking is a function of menthol acting as a conditioned reinforcer, as a consequence of its association with nicotine (and possibly other primary reinforcers, e.g., sweeteners) and because nicotine may further enhance the conditioned reinforcing effects of menthol.

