Following a telephone screen, potentially eligible participants will attend a pre-screen/baseline session either in-person or remotely to confirm eligibility. After completing informed consent, participants will verify age, participants will be asked when they smoked their last cigarette, a baseline carbon monoxide measurement will be taken, and female participants will be asked to verify negative pregnancy status. Participants will then complete a medical history questionnaire, and asked about intentions to quit smoking, mental health with the **Patient Health Questionnaire-9**, and suicide risk using the **MINI Suicide screening** before eligibility can be confirmed. Eligibility determination will be made by the RA based on the inclusion/exclusion criteria. If the participant is deemed initially eligible, the Baseline session will immediately begin. Eligibility criteria will be reviewed by the PI (and the medical monitor, if necessary), to confirm final eligibility for the study, prior to Visit 2. If the participant is eligible after Visit 1 screening procedures, the first baseline session will begin immediately. Participants who are ineligible will be paid \$25 and will not complete the baseline procedures. The RA will make the initial determination of eligibility; final eligibility will be confirmed by the PI (and medical monitor if necessary), prior to Visit 2. Eligible participants will move on to complete the baseline surveys, which is a battery of questionnaires assessing baseline characteristics. After these assessments, the EMA application will be loaded onto the participant's phone or a study-provided phone (at their choosing) and participants will be given a 10-15 minute training, as per the PIs previous EMA studies, on how to use the EMA platform. For 7-days following V1, participants will smoke their usual brand cigarette in their home environment, as per usual, and measurements of cigarettes per day, craving, symptoms of nicotine withdrawal, subjective response, and alternative tobacco use will be assessed twice daily via EMA.

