At the end of V2, participants will receive the first set of assigned research cigarettes and will be asked to smoke those cigarettes in their home environment for 7 days; starting on the day after V2. The ordering of flavor of the research VLNCs to be smoked (menthol and non-menthol) will be counterbalanced and assigned prior to Visit 2 (Individuals who complete the session remotely will be scheduled for a pick-up date to get the VLNCs1). During each 7-day period of exposure, participants will be instructed to switch their usual brand cigarette for the assigned research cigarette and will provide daily data on smoking quantity, craving, withdrawal, subjective response, and alternative tobacco product use via twice daily EMA surveys. We will allow for other tobacco product use without specific instruction to align with the real-world scenario, as these products will exist on the market even if a menthol ban and/or a reduced nicotine standard are enacted. Given the high prevalence of dual and poly-tobacco use in this age group, we will examine change in alternative tobacco product use between conditions as a secondary outcome in exploratory analyses, per Co-I [name]'s and [name]'s previous work. Participants will have a 7-day period wash-out period of return to smoking as usual (own brand of cigarette) between the experimental conditions.

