C.4.f. Research Cigarette Distribution and Accountability. Participants will be given enough cigarettes to accommodate usual smoking patterns until the next visit in 7 days (125% of their baseline cigarettes per day, based on the team's previous work). At V2, participants will report the number of cigarettes smoked per day. Based on this number, staff will calculate the number of SPECTRUM cigarettes needed to provide the participant for each 7-day experimental period (# of own cigs smoked per day x 125% x 7 days). At each in-person visit, research staff will complete a 'Product Accountability Log' with participants to record used and unused cigarettes. Any discrepancies in the product dispensed versus product returned will be discussed and recorded in the log. Participants will be surveyed about desire to quit smoking at each in-person visit. If they endorse that they wish to quit, they will be asked if they still want to receive research cigarettes. If they do not, no study cigarettes will be dispensed and the participant will be retained in the study with no penalty and will continue to complete all subsequent EMAs, the ETM, and the 30-day follow-up. Changes in desire to quit and actual quitting behavior will be examined as an outcome in exploratory analyses, where sample size allows. In her ongoing R01, Co-I [name] dispenses research cigarettes in this manner to 15-19-year-old daily smokers with approvals from the FDA and her institutional IRB.

Measures Descriptions

Participants will complete validated measures from the PhenX Toolkit and the team members' published studies. The following domains will be assessed in the baseline survey: (1) demographics; (2) Tobacco use patterns (age at first use; nicotine dependence (time-to-first use and mFTQ),¹⁴⁵⁻¹⁴⁶ cigarettes per day; alternative tobacco product use; motivation to quit and quit history; peer tobacco use; tobacco marketing/media exposure¹³³⁻¹³⁶; and weekly tobacco expenditure; (3) Self-reported appeal of menthol cigarettes; (4) Harm perceptions of

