Participants will be involved in the study for approximately 2 months. There will be 5 in-person study visits (or virtual sessions) and a total of 21 days of daily monitoring of cigarette smoking behavior. There will be a 30-day follow-up after visit 5, that will be conducted either in person or over the telephone.

4. Describe blinding, including justification for blinding or not blinding the trial.

We considered blinding participants to the nicotine content in the research cigarettes to minimize the possibility that perceptions of these cigarettes may impact ratings of appeal/reinforcement and use behavior (e.g., compensatory behavior). We ultimately chose not blind participants so that we could model real-world conditions in which participants would be aware of the nicotine content of the cigarettes they smoke. [name], our consultant, is taking this same approach (e.g., not blinding participants) in a pilot study conducted as part of her U54. While we know about responses to VLNCs in a blinded scenario, findings from our study will be one of the first to inform VLNC work in an un-blinded scenario with young people.

5. Include justification for inclusion of a placebo or non-treatment group.

N/A. This is not a treatment study.

6. Describe what happens to participants receiving therapy when study ends or if their participation in the study ends prematurely.

N/A. This is not a treatment study.

7. Indicate where the procedures will be completed.

All participant recruitment, enrollment and testing will occur at the research laboratory of the TSET Health Promotion Research Center (HPRC) in Oklahoma City, OK. HPRC has conducted smoking research for the past 5 years.

8. Indicate whether clinically relevant research results, including individual research results, will be disclosed to participants. If so, under what conditions?

Females will be asked to take a pregnancy test at each in-person (or virtual) session prior to smoking, to determine eligibility. If a woman is pregnant, she will be given the results of her test immediately. If the session is completed remotely,

pregnancy tests will be provided to the participant before the session (mailed or curb-side pick-up) and pregnancy will be confirmed prior to beginning a smoking session.

9. Identifiers might be removed and the de-identified information may be used for future research without additional informed consent from the subject.

D. Biospecimens

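### Aim 2 hypothesises about cigarettes per day, but total cigarettes per day is not an Aim 2 outcome, and neither listed count can test the hypothesis against usual brand

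*Combined protocol and SAP*

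**What the plan says.** Section A (Specific Aims), Aim 2, states the hypothesis: "Cigarettes per day, craving reduction, and positive subjective response will be greater for menthol versus non-menthol VLNCs, but lower compared to usual brand". It adds a separate comparison that includes compliance: "Effects of menthol vs non-menthol VLNCs on withdrawal, mood, cigarette compliance, and ATP will be compared".

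Section J.3 (EMA Analyses, Aim 2) gives the primary count outcomes as "b) within-day number of research cigarettes smoked per day; (c) within-day number of non-research cigarettes smoked". The secondary outcomes there are alternative tobacco use, change over days in each outcome, and days abstinent from tobacco. The sum of the two counts appears in neither list.

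The J.3 model is a linear mixed model for the main effect of cigarette type on all primary and secondary outcomes. J.3 names a menthol versus non-menthol VLNC contrast and a comparison of ratings between usual brand and menthol VLNC. It names no usual-brand contrast for counts.

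On timing, the usual-brand week follows Visit 1, when "measurements of cigarettes per day, craving, symptoms of nicotine withdrawal, subjective response, and alternative tobacco use will be assessed twice daily via EMA". The section on Smoking Session 1 (V2) then says: "At the end of V2, participants will receive the first set of assigned research cigarettes". From that point participants are told to replace their usual brand with the assigned cigarette.

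**The concern.** The hypothesis concerns how much people smoke. The two listed counts record which cigarettes they smoke. In the usual-brand week no research cigarettes exist, and in the VLNC weeks participants are told to stop smoking their own. Each count therefore changes between those weeks because of the design, whatever happens to the amount smoked. If the generic main effect of cigarette type is applied to (b) and (c) with usual brand as a level, the design largely fixes the direction of both results. If it is not applied that way, the usual-brand part of the hypothesis has no count analysis at all.

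Consumption also matters to the conclusion that the study wants to draw. Section B (Background and Significance) frames the policy inference as "If smoking menthol VLNCs translates into greater appeal and cigarette consumption relative to smoking non-menthol VLNCs". That sentence is about the two VLNC weeks, where the plan does not say whether (b), (c) or their sum decides.

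**Working it through.** **Inputs from the documents**

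- Section 3 (Duration and number of study visits) gives "a total of 21 days of daily monitoring of cigarette smoking behavior". With two prompts a day (C.5), 21 × 2 = 42 prompts, which matches the 42 calls in the compensation table.
- The usual-brand week has 7 × 2 = 14 prompts, and 14/42 is one third. Count (b) is zero by design at all of them.
- C.4.f sets the research cigarette supply at 125% of baseline consumption.
- The documents give no rate of own-brand smoking in the VLNC weeks, so any such share below is an assumption.

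**Notation.** B is cigarettes per day in the usual-brand week, kB is the total per day in a VLNC week, and s is the own-brand share of that total.

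| | Usual-brand week | VLNC week | Change |
|---|---|---|---|
| (b) research | 0 | kB(1 - s) | +kB(1 - s) |
| (c) non-research | B | kBs | B(ks - 1) |
| (b) + (c) | B | kB | B(k - 1) |

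**Against usual brand**

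- (b) rises for every k > 0 and s < 1.
- (c) falls whenever k < 1/s. At assumed s = 10%, 20% and 30%, total smoking would have to exceed 10, 5 or 3.3 times baseline before (c) rose. At s = 0 it always falls.
- Only the total has the sign of k - 1, which is what the hypothesis is about.

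For a fully compliant participant (s = 0):

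- Whole supply smoked, k = 1.25: (b) goes from 0 to 1.25B, (c) from B to 0, total +25%.
- Consumption halved, k = 0.5: (b) goes from 0 to 0.5B, (c) from B to 0, total -50%.

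With assumed B = 10 and own-brand shares from 50% down to 0%:

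| Total in VLNC week | Change in total | Change in (b) | Change in (c) |
|---|---|---|---|
| 7 | -3 | +3.5 to +7.0 | -6.5 to -10.0 |
| 10 | 0 | +5.0 to +10.0 | -5.0 to -10.0 |
| 13 | +3 | +6.5 to +13.0 | -3.5 to -10.0 |

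The two counts show the same signs whether smoking falls, stays level or rises.

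**Between the two VLNC weeks (illustrative only).** With equal totals, the menthol to non-menthol ratio is (1 - sM)/(1 - sN) for (b) and sM/sN for (c):

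- Own-brand shares 10% and 10%: both ratios are 1.00.
- 10% and 20%: (b) 0.9/0.8 = 1.125 and (c) 0.1/0.2 = 0.50.
- 20% and 30%: (b) 0.8/0.7 = 1.143 and (c) 0.2/0.3 = 0.667.

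With unequal totals, both patterns can occur:

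- Totals 8 (menthol) and 9 (non-menthol), research shares 0.8 and 0.6: (b) 6.4 - 5.4 = +1.0, (c) 1.6 - 3.6 = -2.0, total -1. Here (b) has the wrong sign for consumption.
- Totals 9 and 8, research share 0.7 in both: (b) 6.3 - 5.6 = +0.7, (c) 2.7 - 2.4 = +0.3, total +1. Here all three agree.

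**The case against.** **The planned contrasts are narrower than a three-way test of counts.** The three levels of cigarette type are spelled out in J.2 for Aim 1. J.3 names only the menthol versus non-menthol contrast and a usual-brand comparison of ratings. A reader might infer that the plan commits to testing (b) and (c) against usual brand. The documents do not say so beyond the general main-effect sentence. This stands, but it does not rescue the hypothesis, which then has no specified usual-brand analysis for cigarettes per day.

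**Nothing is forced between the VLNC weeks.** A reader might also infer that the two counts oppose each other in every comparison. They do so by design only against usual brand. Between VLNC weeks it takes a difference in compliance by flavour, for which the documents give no rate. This stands.

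**Count (b) is meaningful in its own right.** Aim 2 is about reinforcement, and C.4.e treats noncompliance as a possible sign of dissatisfaction. Reading (b) as use of the assigned product is legitimate for menthol versus non-menthol VLNCs, and the count should be kept for that. Extending this reading to usual brand would mean comparing own-brand cigarettes in the first week with research cigarettes later. The plan does not state that comparison. At unchanged total smoking (k = 1), own-brand shares of 10%, 20% and 30% would appear as falls of 10%, 20% and 30%, in the hypothesised direction.

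**Overall consumption is not absent from J.3.** It appears as a predicted behaviour in the lagged models, as an adjustment for the previous report, and in the check for participants whose reports do not change. None of these compares consumption across cigarette types.

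**Conclusion.** The point holds and should be fixed before analysis. For the usual-brand part of the Aim 2 hypothesis, the listed outcomes provide no valid test. (b) must rise for anyone who uses research cigarettes, and (c) falls short of a several-fold rise in smoking (more than 1/s times baseline). This follows from the dispensing schedule and the switch instruction. The exception is a participant who uses no research cigarettes, for whom (b) stays at zero and (c) equals the total.

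For menthol versus non-menthol VLNCs the conclusion is weaker. The counts can disagree, and the plan does not say which one decides. The size depends on assumed own-brand shares, so those figures show what is possible and not what is expected.

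This is a gap in outcome specification. Both components of the total are already collected, so it is not a failure of data capture.

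**What to change.** In J.3, add total cigarettes per day, (b) + (c) from EMA, as the outcome that tests the Aim 2 cigarettes-per-day hypothesis. State its contrasts: menthol versus non-menthol VLNC, and each VLNC week versus the usual-brand week. Analyse by assigned week. This includes participants who decline study cigarettes, whom C.4.f already keeps in EMA.

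Keep (b) and (c), but restrict them to the menthol versus non-menthol comparison as outcomes for product-specific use and compliance. Report the research share beside the total. That also serves the compliance comparison announced in Aim 2.

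The cost is one added outcome. No new item or visit is needed, and participants already enrolled are covered. Because the study is unblinded and is to be registered, the addition should be declared as a change to the outcome list, so it is slightly more than a wording edit. The total alone does not separate compliance from amount smoked, which is why the research share has to accompany it.
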